9.3. ADVERSE EVENTS

Adverse events will be analyzed in terms of TEAEs, which are defined as AEs that are newly occurring or worsening from the time of the first dose of study drug. Reported AE terms will be coded using MedDRA version 25.0 or higher. The severity of the toxicities of AEs will be graded according to the NCI CTCAE version 4.03 or higher.

The severity of toxicities of AE is graded as mild (grade 1), moderate (grade 2), severe (grade 3), life-threatening (grade 4), or fatal (grade 5).

The relationship to study treatment is evaluated as definitely related, probably related, possibly related, probably not related, and definitely not related. Events will be classified as related vs non-related. A related AE is an event with a relationship to treatment as definitely related, probably related, or possibly related to study drug; a non-related AE is an event with relationship to treatment as probably not related, or definitely not

Version V3.0

Syneos Health # 1006212

related. If the relationship to the study treatment is missing, the TEAE will be considered to be treatment-related for table summary purposes.

TEAEs will be summarized by SOC and PT and by cohort. Some outputs with TEAEs based on tumor type may be produced for submission purpose. TEAEs with onset after the last dose of the study treatment period are attributed to the treatment received during the treatment period. Both event and subject counts will be summarized. Subject counts will be complemented by percentages calculated using the number of subjects exposed to study drug as the denominator.

The following summaries will be provided:

- An overall summary of the number and percentage of subjects reporting TEAEs, serious TEAEs, grade 3 or higher AEs, death, treatment-related TEAEs, and TEAEs leading to study discontinuation, leading to treatment discontinuation, leading to dose reduction, leading to dose interruption
- TEAEs by SOC and PT (including all severity grades)
- Most common (>= 10%) TEAEs by SOC and PT
- TEAEs by SOC, PT, and worst severity grade
- TEAEs by SOC, PT, and highest relationship (Related, Not Related), for Part C the highest relationship to ALKS and Pembrolizumab will be summarized in separate tables
- ALKS 4230-related TEAEs by SOC and PT
- Pembrolizumab-related TEAEs by SOC and PT
- Serious TEAEs by SOC and PT
- Treatment-related Serious TEAEs by SOC and PT
- Grade 3 or higher related TEAEs by SOC and PT
- TEAE leading to treatment discontinuation by SOC and PT
- TEAE leading to dose reduction by SOC and PT
- TEAE leading to dose interruption by SOC and PT
- Treatment-related TEAE leading to dose interruption
- TEAEs leading to study discontinuation by SOC and PT

Syneos Health # 1006212

- Related TEAEs leading to study discontinuation by SOC and PT
- TEAEs meeting DLT leading to study discontinuation by SOC and PT

The tables will be sorted by overall SOC alphabetically and then, within a SOC, by overall descending frequency of PT based on the subject count for the overall column.

5 PTs including Neutrophil count decreased, Haemoglobin decreased, Platelet count decreased, Supraventricular tachycardia, and Lymphocyte count decreased will be grouped into new PTs as Neutropenia, Anaemia, Thrombocytopenia, Supraventricular extrasystoles, and Lymphopenia respectively. The new grouped SOCs will be Cardiac disorders for the original PT of Supraventricular tachycardia, and Blood and lymphatic system disorders for the rest of 4 original PTs.

For summaries by SOC, PT, and intensity, subject is counted only once at the highest grade for which the event occurred in the SOC and the highest grade for each unique PT within that SOC.

In addition, AEs reported post 30 days of safety follow-up period may be summarized by SOC and PT and/or listed separately.

The original date and time will be shown on all listings of AEs. Listings will be provided for all TEAEs, AEs resulting in death, serious TEAEs, AESIs, DLTs and AEs leading to dose reduction, dose interruption and discontinuation.

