- Any other toxicity or AE not defined above that results in subject removal from the study or discontinuation of dosing by the Investigator (dose delays during Cycle 2 or later are not considered DLTs)

Any laboratory value that meets the DLT criteria as described above must be confirmed with a second laboratory test for DLT criteria to be met.

Subjects without a DLT who receive fewer than 10 doses through C2D15 will be replaced at the same dose level if the minimum number of evaluable subjects has not been reached for the cohort. However, the subject may remain in the study if the Investigator feels the risk/benefit ratio is acceptable.

All DLTs will be summarized by system organ class and preferred term, and by cohort for Part A, and a corresponding listing of DLTs-like will be provided for Part A.

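### SAP 9.3 relabels supraventricular tachycardia as supraventricular extrasystoles, a different rhythm finding, in the preferred-term adverse event tables

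*SAP*

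**What the plan says.** SAP 9.3 tabulates treatment-emergent adverse events (TEAEs) at preferred-term level: "TEAEs will be summarized by SOC and PT and by cohort". It also says: "Both event and subject counts will be summarized". In the tables by intensity, a subject counts once per system organ class (SOC) and once at "the highest grade for each unique PT within that SOC".

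After the list of summaries, 9.3 names five PTs to be regrouped: neutrophil count decreased, haemoglobin decreased, platelet count decreased, supraventricular tachycardia and lymphocyte count decreased. It then gives five target terms in the same order: "Supraventricular tachycardia, and Lymphocyte count decreased will be grouped into new PTs as Neutropenia, Anaemia, Thrombocytopenia, Supraventricular extrasystoles, and Lymphopenia respectively". The next sentence assigns the SOCs: "The new grouped SOCs will be Cardiac disorders for the original PT of Supraventricular tachycardia", with the other four going to the blood and lymphatic SOC.

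SAP 9.2 has a further PT-level table: "All DLTs will be summarized by system organ class and preferred term, and by cohort for Part A". On listings, 9.3 says: "Listings will be provided for all TEAEs, AEs resulting in death, serious TEAEs, AESIs, DLTs", together with events leading to dose changes or discontinuation. For the listings it promises the original date and time. It does not mention the original PT.

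**The concern.** A regrouping of PTs is sound when the terms describe the same clinical event under different codes. Four of these five pairs meet that test. The supraventricular tachycardia pair does not: a tachycardia is a fast rhythm and extrasystoles are extra beats. Replacing the first name with the second changes what the table says happened.

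Incidence and severity of TEAEs is a primary endpoint in Parts A, B and C (SAP 4.1; protocol 6.4), and the PT rows are where the report shows which events occurred. A serious or Grade 3 supraventricular tachycardia would be printed as serious or Grade 3 extrasystoles. Protocol 9.2 names tachycardia, without specifying the supraventricular form, among the infusion-related reactions that may occur with ALKS 4230. An unexplained relabelling of a tachycardia term is therefore poorly placed in this study.

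**Working it through.** The plan states no figure to reproduce. The check is a reading of the mapping, its effect on counting, and a count of the tables it reaches.

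**1. The mapping.** Matching the two lists in SAP 9.3 by position:

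| Original PT | New PT | Relation |
|---|---|---|
| Neutrophil count decreased | Neutropenia | laboratory term to condition |
| Haemoglobin decreased | Anaemia | laboratory term to condition |
| Platelet count decreased | Thrombocytopenia | laboratory term to condition |
| Supraventricular tachycardia | Supraventricular extrasystoles | one rhythm finding to another |
| Lymphocyte count decreased | Lymphopenia | laboratory term to condition |

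The SOC sentence calls supraventricular tachycardia the original PT and sends it to the cardiac SOC. That confirms both the pairing and its direction, and rules out a shuffled list. Neither document mentions a supraventricular term anywhere else, and neither gives a reason for the grouping.

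**2. The effect on counting.** Take one subject with Grade 1 extrasystoles and Grade 3 supraventricular tachycardia.

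- Terms kept apart: one subject at Grade 1 in the extrasystoles row, and one subject at Grade 3 in the supraventricular tachycardia row.
- Rule as written: one subject at Grade 3 in the extrasystoles row and no supraventricular tachycardia row. The event count in the merged row is 2.

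No event is regraded. What changes is the row in which the grade appears and, for a subject with both events, the worst grade shown in that row.

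**3. The tables reached.** SAP 9.3 lists 17 summaries.

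- Two do not name PT: the overall summary, and the one worded "Treatment-related TEAE leading to dose interruption". So 17 − 2 = 15 name PT. If the general SOC-and-PT rule also covers the second of these, the count is 16.
- Of the 15, three take every event: all TEAEs, TEAEs by worst grade, and TEAEs by highest relationship. In Part C the last is split by drug, which makes four tables there.
- The other 12 depend on a filter: the 10% frequency cut-off; ALKS 4230-related; pembrolizumab-related; serious; treatment-related serious; Grade 3 or higher related; leading to treatment discontinuation, dose reduction, dose interruption or study discontinuation; related and leading to study discontinuation; and meeting DLT criteria and leading to study discontinuation. Check: 3 + 12 = 15.
- The pembrolizumab table does not apply to the monotherapy parts, so for Parts A and B the count is 15 − 1 = 14.
- The 10% cut-off is an incidence, so pooling can itself lift the merged row over the threshold when neither term reaches it alone.

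**4. Outside the 17.** SAP 9.2 makes a related Grade 3 cardiac toxicity in the observation window a DLT, and Part A DLTs are tabulated by PT. The SAP does not say whether the 9.3 grouping applies to that table.

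**The case against.** The pairing itself is hard to dispute. The case on the other side is that it matters little and that the remedy presumes intent.

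- **Descriptive tables only.** Protocol 14.2 plans no inferential testing, and total TEAE incidence and DLT determination are unaffected. This stands, and it limits the size of the point.
- **The listings may rescue it.** All TEAEs, serious TEAEs and DLTs are listed. The grouping sentence follows the one on table sorting, so it may be a rule for tables only. The table templates are in a separate document (SAP 15) and could carry a footnote naming the component PTs. All of this is possible and none of it is stated. A correct listing would also leave the table rows wrong.
- **The omission from SAP 11 proves little.** The grouping is not among the declared changes from the protocol, but neither are the four laboratory groupings, and protocol 14.2 expects the SAP to add detail. This objection is fair, and the point does not rest on that omission.
- **The SOC count is not fully settled.** The documents do not state the original SOC of supraventricular tachycardia. That the cardiac SOC row is unchanged is therefore an assumption. If the term came from another SOC, the SOC row would move too.
- **Intent is unknown.** The target term may be a slip, or a pooled arrhythmia category may have been wanted. Neither makes the present wording right. In the first case the name is wrong. In the second, a pooled category should not bear the name of one of its members.

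**Conclusion.** The concern holds. Followed as written, SAP 9.3 prints supraventricular tachycardia under the name of a different rhythm finding. One such TEAE is misnamed in the three unfiltered PT-level summaries for its study part (four tables in Part C) and in each of the 12 filtered summaries it qualifies for. The Part A DLT table may be affected as well.

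The harm is confined to event names, subject counts and worst grades at PT level. It does not alter total TEAE incidence, the grade of any event or DLT determination. Cardiac SOC counts are also unchanged if the original term already sits in that SOC.

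The conclusion rests on the ordinary clinical meaning of the two terms, which the documents do not define. It does not depend on any supraventricular tachycardia having occurred. The rule should be corrected because it governs the presentation of a primary safety endpoint, but it does not threaten the study's main conclusions.

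**What to change.** In SAP 9.3, remove supraventricular tachycardia and supraventricular extrasystoles from the two lists, change the count of regrouped PTs from five to four, and drop the cardiac clause from the SOC sentence. Report supraventricular tachycardia under its own PT and leave the four laboratory groupings as they are. If a pooled category is wanted, give it a neutral name and show both component PTs beneath it.

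It would help to add one line saying whether listings show the original PT and whether the grouping applies to the Part A DLT table.

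The cost is two edited sentences and the matching change in the adverse event derivation. If an earlier data cut for an abstract, presentation or manuscript (SAP 2.2 and 10) used the grouping, it needs a short note explaining the difference.

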9.4. LABORATORY EVALUATIONS

Clinical laboratory data are collected at the time points specified in study procedures and flow chart. The assessments are presented in the table on next page.

Alkermes Protocol # ALK4230-A101

Version V3.0

Syneos Health # 1006212

Hematology	Biochemistry	Urinalysis
 Hematocrit Hemoglobin Red blood cell count Total and differential (absolute) white blood cell count Platelets 	General Chemistry Albumin Bicarbonate Calcium Chloride Creatine phosphokinase Glucose Magnesium 	 Bilirubin Color and appearance Glucose Ketones Leukocytes Nitrite Occult blood pH
 International normalized ratio Partial thromboplastin time / Activated partial thromboplastin time 	 Phosphorus Potassium Sodium Total protein Uric acid Liver Function Tests Alanine transferase Alkaline phosphatase Aspartate transferase Lactic dehydrogenase Total bilirubin Renal Function Tests Blood urea nitrogen Creatinine Thyroid Test Thyroid Test Thyroid-stimulating hormone Serum Tumor Marker CA125 (ovarian cancer subjects only) CA19-9 (gastric and pancreatic cancer subjects only) PSA (prostate cancer subjects only) CEA (colorectal cancer subjects only) 	 Protein Specific gravity Urobilinogen Microscopic examination of sediment, only if urinalysis dipstick results are abnormal. Microscopic examination is not needed if urinalysis is abnormal for bilirubin, glucose, or ketones. Microbiology (as Applicable) Blood Urine Other

Version V3.0

Syneos Health # 1006212

A serum or urine pregnancy test will be administered to all women of childbearing potential. At the screening visit, results must be negative for the subject to be eligible for the study.

Separate analysis table for CA125 for ovarian pts will be displayed.

In addition, the hematology, coagulation, and chemistry laboratory parameters will be graded according to NCI CTCAE (version 5.0 or higher) where applicable.

Subjects who meet the potentially clinically significant (PCS) criteria in selected lab parameters will be summarized by treatment cohort, the PCS is defined as Grade 3 or above per CTCAE.

Lab shift table of CTCAE grade (1 to 5) will be summarized from baseline grade to minimum, maximum, and final grade.

Number of subjects who meet the following liver function test criteria will be summarized and corresponding listing will be presented:

• An elevated aspartate aminotransferase (AST) or alanine aminotransferase (ALT) laboratory value that is ≥3× the upper limit of normal (ULN) and an elevated total bilirubin laboratory value that is ≥2× ULN and an alkaline phosphatase laboratory value that is <2× ULN within 3 days.

The corresponding listing will present all AST, ALT, total bilirubin, and alkaline phosphatase laboratory data for any subject meeting the aforementioned criteria at least one time.

Listings will be provided for the hematology, coagulation, chemistry, urinalysis, and pregnancy tests results.

9.5. VITAL SIGNS

Vital signs assessments include respiratory rate, temperature, blood pressure, body weight, and heart rate.

The vital signs assessments will be graded according to NCI CTCAE (version 5.0 or higher) where applicable.

Subjects who meet the potentially clinically significant (PCS) criteria in vital sign will be summarized by treatment cohort, the PCS is defined as Grade 3 or above per CTCAE.

Vital signs shift table of CTCAE grade (1 to 5) will be summarized from baseline grade to minimum, maximum, and final grade.

Version V3.0

Syneos Health # 1006212

9.6. ECG

The standard 12-lead ECGs will be performed in triplicate 5 minutes apart at all time points outlined in the protocol. The mean value will be used for summary purposes.

The QTcF Intervals fulfilling grade 3 or above per CTCAE will be tabulated separately.

Subjects who meet the potentially clinically significant (PCS) criteria in the QTcF will be summarized by treatment cohort, the PCS is defined as QTcF >=501 msec or >60 msec change from baseline.

The QTcF shift table of CTCAE grade (1 to 5) will be summarized from baseline grade to minimum, maximum, and final grade.

9.7. EASTERN COOPERATIVE ONCOLOGY GROUP (ECOG) PERFORMANCE STATUS

The ECOG performance status assesses the subjects' activity status and will be assessed at the time points specified in Table 3, Table 4, Table 5, Table 6, and Table 7. Possible scores are 0 to 5. Descriptions of activity status are presented in Table 12. The data will be listed.

Grade	Description
0	Fully active, able to carry on all predisease performance without restriction
1	Restricted in physically strenuous activity but ambulatory and able to carry out work of a light or sedentary nature (eg, light house work, office work)
2	Ambulatory and capable of all self-care but unable to carry out any work activities; up and about more than 50% of waking hours
3	Capable of only limited self-care; confined to bed or chair more than 50% of waking hours
4	Completely disabled; cannot carry on any self-care; totally confined to bed or chair
5	Dead

Table 12: Eastern Cooperative Oncology Group Performance Statu

Source: Oken et al, 1982.

9.8. PHYSICAL EXAMINATION

A full physical examination will be performed at screening and end-of-treatment visits. If possible, a brief physical examination focused on areas of disease or AE will be assessed at Day 1 of each cycle. These data will be available for reference.

Version V3.0

Syneos Health # 1006212

10. INTERIM ANALYSES

No formal interim analysis is planned with respect to stopping the study early or for lack of antitumor activity purposes. Interim data cuts will be conducted to support abstract submissions, conference presentations, and/or manuscript(s).

Responses in each N1 stage will be assessed to determine whether progression to the N2 stage is warranted, based on criteria defined in Section 3.6.

Version V3.0

Syneos Health # 1006212

11. CHANGE FROM ANALYSIS PLANNED IN PROTOCOL

Durable response rate is listed as secondary endpoint but no summaries are planned.

Analysis based on irRC and iRECIST will not be performed as the iRECIST was implemented during the middle of the study conduct to replace irRC. The sites have not consistently record the iRECIST data which could provide misleading information.

The protocol stated that the PFS analysis would be only performed for Part B and Part C (Cohorts 5-7). The additional PFS analysis in ovarian patients from the PD-L1 unapproved cohort will be conducted as ovarian is identified as one of tumor types to advance further clinical development in Nemvaleukin in combination with Pembrolizumab.

Version V3.0

Syneos Health # 1006212

12. **REFERENCE LIST**

International Conference on Harmonisation of Technical Requirements for Registration of Pharmaceuticals for Human Use. ICH Harmonised Tripartate Guideline: Nonclinical evaluation for anticancer pharmaceuticals. S9. http://www.ich.org/fileadmin/Public_Web_Site/ICH_Products/Guidelines/Safety/S9/St ep4/S9_Step4_Guideline.pdf.

Published October 29, 2009. Accessed 01 February 2016.

US Department of Health and Human Services, National Institutes of Health, National Cancer Institute. Common Terminology Criteria for Adverse Events (CTCAE) Version 4.0. http://evs.nci.nih.gov/ftp1/CTCAE/CTCAE_4.03_2010-06-

14_QuickReference_8.5x11.pdf. Published 28 May 2009 (v4.03 14 June 2010). Accessed 01 February 2016.

13.1. GENERAL CONSIDERATIONS

- A separate SAS program will be created for each output.
- Each output will be stored in a separate file.
- Output files will be delivered in Word format.
- Numbering of TFLs will follow International Council for Harmonization of Technical Requirements for Pharmaceuticals for Human Use (ICH) E3 guidance.

13.2. TABLE, LISTING, AND FIGURE FORMAT

13.2.1. General

- All TLFs will be produced in landscape format, unless otherwise specified.
- All TLFs will be produced using the Courier New font, size 8.
- The data displays for all TLFs will have a minimum 1-inch margin on all 4 sides.
- Headers and footers for figures will be in Courier New font, size 8.
- Legends will be used for all figures with more than 1 variable, group, or item displayed.
- TLFs will be in black and white (no color), unless otherwise specified.
- Specialized text styles, such as bolding, italics, borders, shading, and superscripted and subscripted text, will not be used in the TLFs, unless otherwise specified. On some occasions, superscripts 1, 2, or 3 may be used (see below).
- Only standard keyboard characters will be used in the TLFs. Special characters, such as non-printable control characters, printer-specific, or font-specific characters, will not be used. Hexadecimal-derived characters will be used, where possible, if they are

Version V3.0

Syneos Health # 1006212

appropriate to help display math symbols (eg, μ). Certain subscripts and superscripts (eg, cm², C_{max}) will be employed on a case-by-case basis.

• Mixed case will be used for all titles, footnotes, column headers, and programmersupplied formats, as appropriate.

13.2.2. Headers

• All output should have the following header at the top left of each page:

Alkermes, Inc.

Protocol ALK4230-A101

- All output should have Page n of N at the top or bottom right corner of each page. TLFs should be internally paginated in relation to the total length (ie, the page number should appear sequentially as page n of N, where N is the total number of pages in the table).
- The date output was generated should appear along with the program name as a footer on each page.

13.2.3. Display Titles

• The title will be centered. The analysis set will be identified on the line immediately following the title. The title and table designation will be single spaced. A solid line spanning the margins will separate the display titles from the column headers. There will be 1 blank line between the last title and the solid line as per the example below.

Table x.y.z First Line of Title Second Line of Title if Needed ITT Analysis Set

13.2.4. Column Headers

- Column headings will be displayed immediately below the solid line described above in initial upper-case characters.
- In the case of efficacy tables, the variable (or characteristic) column will be on the far left followed by columns for cohorts and total column (if applicable).
- For numeric variables, include "unit" in column or row heading when appropriate.

Syneos Health # 1006212

- Analysis set sizes will be presented for each cohort in the column heading as (N=xx) (or in the row headings if applicable). This is distinct from the 'n' used for the descriptive statistics representing the number of non-missing subjects in the analysis set.
- The order of cohorts in the Part A tables and listings will be by the order of dose escalation, as dose level: 0.1 µg/kg, 0.3 µg/kg, 1 µg/kg, 3 µg/kg, 6 µg/kg, 10 µg/kg, 15 µg/kg, overall (if applicable). The order of cohorts in the Part B tables and listings will be: Melanoma, RCC, overall (if applicable). The order of cohorts in the Part C tables and listings will be: PD-1 unapproved tumor types, PD-1 approved tumor types (PD-1/L1 pretreated), PD-1 approved tumor types (PD-1/L1 treatment naïve), Rollover, overall (if applicable).

